## **7.0 Stereotactic Body Radiotherapy Treatment Delivery**

### **7.1 Premedication**

The decision to premedicate a patient prior to head and neck SBRT is at the discretion of the treating radiation oncologist. Most patients typically do not need premedication. The following are a list of agents that have been used by some investigators to potentially reduce patient discomfort and possibly prevent acute and/or late toxicity if used as premedication prior to SBRT.

- 7.1.1 Corticosteroids (Decadron 4 mg PO or equivalent) 15-60 minutes prior to each fraction for the intended purpose of modulating immediate inflammatory effects.
- 7.1.2 Analgesic premedication to avoid general discomfort during long treatment durations.
- 7.1.3 Anti-anxiety medication for patient comfort during long treatment duration

### **7.2 Treatment**

- 7.2.1 The medical physics staff will perform routine quality assurance checks on the treatment machine to ensure that the mechanical isocenter stability is within specification (ie. diameter  $\leq 1.5$  mm).
- 7.2.2 The medical physics staff will perform patient-specific quality assurance measurements to ensure that the treatment plan is deliverable and that the dose distribution is accurate.
- 7.2.3 The patient will be positioned in the custom immobilization device on the Hexapod® treatment couch and aligned with the in-room lasers.
- 7.2.4 Daily CT localization of the GTV isocenter is required prior to each fraction. Once the patient is properly positioned, a cone-beam CT of the treatment area is acquired, fused, and aligned to the treatment planning CT. Translational and rotational adjustments of patient positioning are performed as indicated. If adjustment are required, an orthogonal (ex. AP and LATERAL) set of electronic portal images is then obtained prior to treatment to confirm proper alignment of the isocenter.
- 7.2.5 Either multiple coplanar or noncoplanar static gantry angle intensity-modulated fields or rotational arcs will be utilized.
- 7.2.6 Only photon (x-ray) beams will be used, preferably in energies of 6 MV.

## **8.0 Drug Therapy**

- 8.1** The use of chemotherapy is left to the discretion of the medical oncologist.
- 8.2** Chemotherapy agents during radiation is not allowed. If chemotherapy is planned, it should ideally not have been given within 2 weeks of starting radiation and should not resume until at least 2 weeks after completing radiation.

## **9.0 Patient Assessment**

### **9.1 Study Parameters**

The following are suggested patient follow-up intervals and evaluations that may be performed to either assess for treatment toxicity or tumor response to SBRT:

Assessment	Pre-Rx	Post-Rx 6 wk	Post-Rx 3 mo	Post-Rx 6 mo	Post-Rx 9 mo	Post-Rx 1 yr
History & Physical	X	X	X	X	X	X b
Weight	X	X	X	X	X	X b
Disease status	X	X	X	X	X	X b
Toxicity Assessment		X	X	X	X	X b
Pregnancy test	X a					
CT and/or MRI (head and neck)	X	X	-	X	-	X b

a if clinically appropriate

b clinical examination, late toxicity, and disease status assessment at 3 month intervals for first year, then at the discretion of the treating radiation oncologist

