Chordomas are locally aggressive and destructive tumors with high recurrence rates. Chondrosarcomas arise from the skull base and tend to affect lower cranial nerves. Complete surgical resection is rarely feasible for these lesions. Various modalities of fractionated radiation therapy have been used to increase local control. Stereotactic body radiotherapy delivers more conformal radiation with greater radiobiological effect than conventional radiation therapy. Compared to conventional radiation therapy, SBRT may reduce toxicity to normal surrounding structures and potentially cause fewer complications. Martin et al. from the University of Pittsburgh reported on 28 patients treated with SBRT as a boost after external beam radiation or as the sole treatment. The median follow up was 7 years. The five year local control rate for chondrosarcomas was 80%. The five year local control rate for chordomas was 62%. One patient developed mild dizziness and nausea which was controlled with a two week course of corticosteroids. No long term side effects were reported. The authors concluded that SBRT is an important treatment option for chordomas and chondrosarcomas(12-15).

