### **2.2 Study Design**

**2.2.1** Single site, non-randomized, prospective, phase IV study

**2.2.2** Composed of 3 patient groups:

- Benign tumors, such as paraganglioma (ex. Glomus jugulare, glomus tympanicum, carotid body tumor) chordoma, chondrosarcoma, as the sole treatment or to gross residual disease after maximal safe resection
- Malignant tumors, such as nasopharynx cancer and squamous cell carcinoma, after initial external beam radiation (Residual Disease Group)
- Unresectable malignant tumors, such as nasopharynx cancer and squamous cell carcinoma, adenocarcinomas, and sarcomas which are recurrent after prior radiation (Primary RT Group)

**2.2.3** Data collected will include baseline patient demographics, pathology data, radiation therapy procedure, tumor recurrence data, and toxicities.

**2.2.4** Follow up data will be collected during the patient's standard office visits. The anticipated duration of this study is 5 years.

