### **2.3 End Points**

**2.3.1** Primary endpoints will be local control rate and complication rate

- Local recurrence is defined as cancer recurrence within the target volume.
- Local control rate will be evaluated by imaging techniques, physical exam and biopsy, if applicable.
- Evaluation of complication rates (see Section 9.3 for definitions)

**2.3.2** Secondary endpoint will be overall survival

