## **10.4 Justification of the Study**

Patients who have locally recurrent or persistent malignant head and neck cancer after definitive conventionally fractionated radiation therapy pose a therapeutic challenge since complete surgical resection is often not feasible and surrounding critical normal tissues have typically received close to maximum tolerable radiation doses. High dose, precisely targeted radiation with stereotactic body radiotherapy, which delivers minimal additional radiation dose to nearby normal tissues can produce durable local control and palliation of local symptoms such as pain. In addition, some benign head and neck tumors which are located near the skull base and/or involve critical vasculature also pose a surgical challenge. These tumors appear to have a reasonably high local control probability with radiation therapy. SBRT is advantageous in this setting by limiting the dose to adjacent normal tissues in patients who otherwise have a long life expectancy.

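### No toxicity grade is taken before SBRT, so late effects of earlier radiation cannot be reliably separated from SBRT complications

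*Protocol*

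**What the plan says.** Protocol section 2.3 states: "Primary endpoints will be local control rate and complication rate". Section 2.2 describes a single-site, non-randomized study in three groups.

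The schedule in section 9.1 has six columns: pre-treatment, 6 weeks, 3, 6 and 9 months, and 1 year. The toxicity row reads "Toxicity Assessment X X X X X b", so grading starts at 6 weeks. The rows for history and physical, weight and disease status are marked in all six columns. The whole table is introduced as "suggested patient follow-up intervals and evaluations that may be performed".

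Section 4.0 asks for a history that covers earlier radiation and chemotherapy, and for an examination that locates and measures the lesion. It asks for no grading. The demographic form (Appendix IV) and the treatment form (Appendix V) have no field for existing symptoms or grades. The follow-up form (Appendix VI) is the only one that takes CTC grades. It has columns for grade, timing, treatment and comments, but none for a baseline grade, and its heading restricts entries to events related to radiation.

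On who enters, section 2.2 places one malignant group "after initial external beam radiation (Residual Disease Group") and describes the tumours of the other as ones "which are recurrent after prior radiation (Primary RT Group"). Section 10.4 says of persistent or recurrent malignant disease that "surrounding critical normal tissues have typically received close to maximum tolerable radiation doses".

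**The concern.** A patient irradiated before SBRT may arrive with a dry mouth or hearing loss from that earlier course. If the deficit is first graded at 6 weeks, the study record holds a grade but nothing graded to compare it with. The deficit may then be counted as an SBRT complication although it has not changed, or a real worsening may be put down to the earlier course. With no control group, the background level of such deficits cannot be read from the study either.

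An analysis plan can set the rule for what counts as a complication, but it cannot supply a grade that was never collected. Schedule and forms are fixed in this protocol, so the gap has to be closed here.

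**Working it through.** The plan gives no figure on this point to reproduce, so the check is mainly a comparison of the document's parts.

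1. **Schedule.** The weight row in 9.1 has six marks and the toxicity row has five, with the empty cell at pre-treatment. The pregnancy-test row has its single mark at pre-treatment, so the columns appear to be aligned and the blank does not look like a text-extraction fault.

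2. **Forms.** Appendix IV records performance status, stage, tumour size, metastatic status, earlier radiation (yes, with an explanation) and earlier chemotherapy. Appendix V records dose and premedication. Neither holds a symptom grade. Appendix VI holds grades, but only at follow-up visits. Weight loss is an exception: section 9.1 schedules weight before treatment, and Appendix III grades the loss as a percentage of baseline.

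3. **Scales.** In Appendix III, xerostomia is graded by present symptoms, diet and saliva flow, and hearing by the need for an aid or intervention. Neither scale asks about change. An unchanged old deficit therefore meets a grade definition at 6 weeks.

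4. **What the follow-up form filters.** Its heading excludes, in principle, an unchanged deficit caused by tumour or surgery. It does not exclude a late effect of the earlier course, which is also related to radiation. The timing and comments columns let an investigator say so, but nothing asks for it.

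5. **Scales that are absent.** Appendix III prints no scale for several Appendix VI items, among them cranial nerve neuropathy and vocal cord paralysis. A remedy that only says to use the same scale would not work for these.

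**Illustration only; every input is assumed.** For one form item, let q be the true rate of new or worse events, p the share of patients who enter with that item from earlier radiation (independent of q), and f the share of unchanged old deficits recorded as SBRT complications.

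Recorded rate = q + f × p × (1 − q)

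| q = 10% | f = 0 | f = 10% | f = 25% | f = 50% |
|---|---|---|---|---|
| p = 10% | 10% | 10.9% | 12.3% | 14.5% |
| p = 30% | 10% | 12.7% | 16.8% | 23.5% |

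For example, 0.10 + 0.25 × 0.30 × 0.90 = 0.1675. In the roughly 50 patients named in Appendix I, that is 50 × 0.1675 = 8.4 recorded against 50 × 0.10 = 5 true.

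In the other direction, if a share g of worsening in already affected patients is dismissed as old, the recorded rate is q − g × p × q. With q = 10% and p = 30%, g = 50% gives 8.5% and g = 100% gives 7%. With p = 10% the results are 9.5% and 9%.

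The table shows only that the result depends on f and g, which the plan leaves to recollection and individual attribution. If attribution were perfect (f = g = 0), there would be no bias.

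**The case against.** The strongest reply is that the plan already has partial safeguards. The history and physical before treatment can capture an existing deficit, the demographic form asks about earlier radiation, and the follow-up form is limited to radiation-related events. Much of this stands. Some baseline deficits could be reconstructed from the chart, though ungraded and less reliably than by prospective grading. Fatigue, whose first grade is defined relative to baseline, needs knowledge of the earlier state rather than an earlier grade.

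Several stronger readings are tempting but not supported:

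- **All old deficits will be counted.** Benign tumours may be treated by applying SBRT "to gross residual disease after maximal safe resection", and the Introduction says "Chondrosarcomas arise from the skull base and tend to affect lower cranial nerves". A reader might infer that such deficits inflate the rate as well. The form's heading excludes them in principle when unchanged, so the real ambiguity lies with late effects of earlier radiation.
- **The protocol says deficits are present.** Section 10.4 speaks of dose close to tolerance, not of observed deficits. They are plausible at entry, not documented.
- **Every chronic item is affected alike.** Appendix VI lists xerostomia as acute. The lymphatics scale in Appendix III refers to a baseline, but Appendix VI has no such item. The argument about scales of present state is shown here only for xerostomia and hearing.
- **Over-counting must outweigh under-counting.** In the illustration this follows from the formula whenever q is below 50%. It is not evidence about this trial. Independence of p and q is also doubtful, since previously irradiated patients may have both more old deficits and more new events.

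It is also fair that the rule for counting events may sit in an analysis plan. That leaves the need to collect the baseline untouched.

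**Conclusion.** The point holds as a gap in data collection. The protocol neither schedules nor records a toxicity grade before SBRT. In previously irradiated patients, late effects of the earlier course therefore cannot be reliably separated from SBRT complications, most clearly for xerostomia and hearing.

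That the schedule cell and the form fields are missing is certain. That this will bias the complication rate, in which direction and by how much, is unknown: the documents give neither the frequency of deficits at entry nor an expected complication rate. A reader might infer from the illustration that the rate will be overstated by a definite amount, but its inputs are assumptions. Nor does the point make the endpoint impossible to compute; it makes attribution weaker than it need be. It concerns the complication rate of section 2.3, and the illustration does not carry over to the serious-adverse-event incidence in section 10.5. The change should be made, because a baseline that was not graded before SBRT cannot be graded prospectively afterwards.

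**What to change.** - In section 9.1, mark Toxicity Assessment at the pre-treatment visit. State that this baseline grading and the matching follow-up toxicity grading are required. A required baseline set against optional follow-up would not secure the comparison.
- At the history and physical already scheduled before treatment, record baseline status once for the Appendix VI items, from any cause, on the same CTCAE v3.0 scale as at follow-up.
- For items with no scale printed in Appendix III, such as cranial nerve neuropathy and vocal cord paralysis, either add the CTCAE v3.0 scale or record present or absent with a description, in the same way at both times.
- Add a baseline-grade column to the follow-up form so that new or worsened events can be identified. The counting rule itself can stand in the analysis plan.

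The cost is one extra form page per patient at an existing visit, a short addition to section 9.1, one column on the follow-up form and, if that option is chosen, the added scales in Appendix III. No new visit or procedure is needed.

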### **9.2 Response Criteria**

- 9.2.1** CT scan of the soft tissues of the neck with IV contrast (MRI may be used)  
- Local recurrence is defined as tumor recurrence within the planning target volume. If necessary, a PET/CT scan may be used to aid in diagnoses local tumor recurrence.
- 9.2.2** PET/CT scan  
- May be obtained at the discretion of the treating radiation oncologist if there is uncertainty on the diagnostic CT scan as to the disease status in the head and neck.
- 9.2.3** A local recurrence is defined as cancer recurrence within the planning target volume.
- 9.2.4** Distant metastases will not be considered a treatment failure unless accompanied by local recurrence.

### **9.3 Toxicity**

**9.3.1** The investigator will report and record all serious adverse events that occur. Adverse events should be reported using the CTC grading system (Appendix III).

**9.3.2** Examples of anticipated acute adverse events include:

- General malaise
- Radiation dermatitis – dryness, tanning, redness, itching
- Localized hair loss
- Mucositis
- External otitis
- Otitis Media
- Xerostomia
- Mastoiditis

- Weight loss
- Pharyngitis
- Vertigo

**9.3.3** Examples of anticipated late adverse events include:

- Radionecrosis of the temporal bone, skull base, mandible
- Radionecrosis of brain tissue
- Soft tissue necrosis
- CVA
- Cranial nerve neuropathy
- Ipsilateral hearing loss
- Vocal cord paralysis
- Nasal hemorrhage
- Localized skin fibrosis, edema, and/or ulceration
- Radiation-induced malignancy (ex. Fibrosarcoma)

**9.3.4** Reporting of unanticipated or serious adverse events will be reported according to the institutions IRB policy. An unanticipated adverse effect is defined as follows:

Any serious adverse effect on health or safety or any life-threatening problem or death caused by, or associated with, stereotactic body radiotherapy, if that effect, problem, or death was not previously identified in nature, severity, or degree of incidence in the investigational plan or application (including a supplementary plan or application), or any other unanticipated serious problem associated with a treatment that relates to the rights, safety, or welfare of subjects.

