### **2.1 Hypothesis**

**2.1.1** For selected patients with primary or recurrent head and neck tumors, stereotactic body radiotherapy (SBRT) is technically feasible with acceptable complication rates.

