### **6.3 Normal Tissue Dose Constraints**

**6.3.1** Normal tissue dose constraints will depend on whether nearby critical normal tissues have received prior external beam radiation, what dose they received, and the time between prior radiation and the current SBRT treatment course. These dose limits will ultimately be determined by the treatment radiation oncologist. For patients who have received prior radiation therapy, every effort should be taken to limit the cumulative doses to adjacent critical normal tissues as follows based on standard fractionation schemes (1.8-2 Gy per day):

Spinal cord –  $D_{max} = 50$  Gy

Brainstem –  $D_{max} = 60$  Gy

Optic Nerves –  $D_{max} = 50$  Gy

Optic Chiasm -  $D_{max} = 54$  Gy

**6.3.2** For patients in whom SBRT is planned following initial standard-fractionation wide-field external beam radiation (Residual Disease Group), the initial radiation course should be designed to limit exposure to adjacent critical normal tissues as follows:

Spinal cord –  $D_{max} = 40$  Gy

Optic Apparatus –  $D_{\max} = 50$  Gy

Brainstem –  $D_{\max} = 50$  Gy

- 6.3.3** For patients who have not received prior radiation therapy, the following dose limits should be maintained:

Structure	1 Fraction	3 Fractions	5 Fractions
Optic Chiasm	8 Gy $D_{\max}$	12 Gy $D_{\max}$	14 Gy $D_{\max}$
Optic Nerve	8 Gy $D_{\max}$	12 Gy $D_{\max}$	14 Gy $D_{\max}$
Brainstem	14 Gy $D_{\max}$	22 Gy $D_{\max}$	27 Gy $D_{\max}$
Spinal Cord	8 Gy to < 0.5 cc 10 Gy to < 0.3 cc 12 Gy to < 0.15 cc	18 Gy $D_{\max}$	22 Gy $D_{\max}$
Brachial Plexus	14 Gy $D_{\max}$	24 Gy $D_{\max}$	25 Gy $D_{\max}$
Internal Carotid Artery in Cavernous Sinus	25 Gy $D_{\max}$	32 Gy $D_{\max}$	35 Gy $D_{\max}$
Oculomotor Nerves in Cavernous Sinus	30 Gy $D_{\max}$	32 Gy $D_{\max}$	35 Gy $D_{\max}$
Esophagus	15 Gy $D_{\max}$	24 Gy $D_{\max}$	30 Gy $D_{\max}$
Skin	15 Gy $D_{\max}$	24 Gy $D_{\max}$	30 Gy $D_{\max}$

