## **10.2 Minimization of Risks**

Although the risks outlined in Section 9.3 may occur, the likelihood of serious events occurring is considered uncommon as long as certain precautions are taken. The potential risks have been minimized by strict compliance with normal tissue dose constraints as described in Sections 6.3.

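### Complication rate is a primary endpoint and its acceptability is the hypothesis, yet the visible protocol states no tolerable rate, no scheduled review of accumulated serious toxicity and no count that pauses accrual

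*Protocol*

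**What the plan says.** **Hypothesis and endpoint.** Section 2.1.1 proposes that, in selected patients, "stereotactic body radiotherapy (SBRT) is technically feasible with acceptable complication rates". Section 2.3.1 states: "Primary endpoints will be local control rate and complication rate". It then refers the reader onward: "Evaluation of complication rates (see Section 9.3 for definitions".

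**What 9.3 supplies.** Section 9.3.1 obliges the investigator to record and report every serious adverse event and calls for CTC grading using Appendix III. Sections 9.3.2 and 9.3.3 list examples of acute and late events. On oversight, 9.3.4 says: "Reporting of unanticipated or serious adverse events will be reported according to the institutions IRB policy". It defines an unanticipated effect partly as one that "was not previously identified in nature, severity, or degree of incidence in the investigational plan or application".

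**Expected risk.** Section 10.2 says that "the likelihood of serious events occurring is considered uncommon as long as certain precautions are taken", and continues: "The potential risks have been minimized by strict compliance with normal tissue dose constraints as described in Sections 6.3".

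**Dose limits.** For previously irradiated patients, 6.3.1 gives cumulative maximum-dose goals of 50 Gy (spinal cord), 60 Gy (brainstem), 50 Gy (optic nerves) and 54 Gy (chiasm). Section 6.3.2 gives 40 Gy (cord), 50 Gy (optic apparatus) and 50 Gy (brainstem) for the initial course in the Residual Disease Group. But 6.3.1 also says: "These dose limits will ultimately be determined by the treatment radiation oncologist".

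**Use of the data.** Section 10.5.2 plans to calculate the incidence of any serious adverse events. Section 9.4 covers withdrawal of individual patients. The follow-up form (Appendix VI) sends individual serious event reports to the HIC. Appendix I expects about 50 participants; 2.2.2 defines three groups without sizes.

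**The concern.** A hypothesis of acceptable complication rates needs a rate against which to judge the result. If none is stated in advance, what counts as acceptable can be settled once the result is known.

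The larger matter is conduct. Two of the three groups in 2.2.2 are treated after earlier radiation, and the listed late harms include brain radionecrosis, stroke and soft tissue necrosis. Reports handled one at a time can each look explicable while the total is too high. Nothing in the visible protocol requires anyone to look at the total at a set time, or says what total should halt entry. A pause rule acts while patients are being treated, so an analysis plan applied afterwards cannot supply it.

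**Working it through.** **1. Reading the sections together.** The protocol gives no tolerable rate, error rate or boundary, so there is no figure of its own to reproduce.

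| Question | Where one would look | What is there |
|---|---|---|
| What rate is acceptable? | 2.1.1, 2.3.1, 9.3, 10.2, 10.5 | No number; 10.2 calls serious events uncommon |
| When is the total reviewed? | 9.3.4, 10.5.2, Appendix VI | Single reports under IRB policy; a rate to be calculated, with no timing |
| What total pauses accrual? | 9.3, 9.4, 10.5 | Nothing; 9.4 concerns single patients |
| Are dose limits binding after prior radiation? | 6.3.1, 6.3.2, 10.2 | Numeric goals to be pursued with every effort, final limits left to the oncologist; 10.2 assumes strict compliance |

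**2. What is exposed.** With N = 50 (Appendix I), expected affected patients = 50 × p: 5 at 10%, 10 at 20%, 15 at 30%. Exact 95% intervals at n = 50 are 3.3–21.8% for 5 events, 10.0–33.7% for 10 and 17.9–44.6% for 15. Without a benchmark, none of these can be called acceptable or unacceptable.

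**3. An illustrative pause rule.** Assume 10% is tolerable. Pause if the number affected reaches 4 among the first 10 patients, 5 among the first 20, 7 among the first 30 or 8 among the first 40.

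Let f(k) be the probability of k affected patients with no earlier crossing. At each look, f_new(k) = Σ f_old(j) · C(10, k−j) · p^(k−j) · (1−p)^(10−k+j). The mass at or above the limit is the chance of pausing at that look, and it is then removed.

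First look at p = 0.10: 1 − (0.3487 + 0.3874 + 0.1937 + 0.0574) = 0.0128.

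| True rate | Look 10 | Look 20 | Look 30 | Look 40 | Total, first 40 only | Adding 10/50 |
|---|---|---|---|---|---|---|
| 10% | 0.0128 | 0.0343 | 0.0090 | 0.0172 | 0.073 | 0.078 |
| 20% | 0.1209 | 0.2589 | 0.0970 | 0.1410 | 0.618 | 0.670 |
| 30% | 0.3504 | 0.4178 | 0.1066 | 0.0799 | 0.955 | 0.975 |

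(The 30% total is 0.9547 before rounding.) Patients 41–50 need an explicit rule: carrying the limit of 8 on to patient 50 raises the pause chance at a true 10% to 14.0%.

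**4. Limits of the rule, first 40 counted.**
- *Excess in one group, prompt events.* With 16 of 50 at 30% and the rest at 5%, the mean rate is (16 × 0.30 + 34 × 0.05)/50 = 6.5/50 = 13%. The pause chance is about 18% by simulation and 19% from the recursion at 13%.
- *Excess in both previously irradiated groups, prompt events.* With 33 of 50 at 30% and the rest at 5%, the mean rate is (9.9 + 0.85)/50 = 21.5%, and the pause chance is about 70%.
- *Late onset.* Assume exponential onset with a median of 12 or 24 months, even accrual over 3 or 5 years, and counts kept open until accrual closes. The pause chance is 29–86% with everyone at 30%, 10–52% with 33 of 50, and about 1.5–11% with 16 of 50. Death as a competing event is not modelled.
- *By-group table, prompt events.* With groups of 16/17/17 at 30%/5%/5%, some group shows 4 or more affected patients in about 57% of trials, against 11% if all are at 10%. The table adds information but does not settle the matter.

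**The case against.** Several things count against the point.

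- A reader might infer that serious toxicity goes unrecorded or unwatched. The text does not support that. Section 9.3.1 makes recording of all serious events mandatory and requires grading, and individual reports go to the IRB/HIC. The gap is confined to the accumulated total.
- A reader might infer that previously irradiated patients have no dose limits. They have numeric goals in 6.3.1 and 6.3.2, section 6.2.2 asks that constraints be kept, and Table 2 of the Treatment Form records prior plus new maximum dose by organ. What stands is narrower: the final limit is the oncologist's, so the strict compliance on which 10.2 relies is not assured.
- A reader might infer that the incidence limb of the 9.3.4 definition has no reference at all. Sections 9.3, 10.1 and 10.2 give no incidence, but the definition also refers to an application that is not shown, so complete absence is not established.
- The IRB policy is not shown and may require cumulative review. That could close the review gap, but would not by itself state the rate that the hypothesis needs.
- The endpoint's grade cut-off and method of summary may sit in an analysis plan; they are not counted here. The pause rule is different because it governs accrual.
- All tolerable rates, group sizes and onset times above are assumed, and the pooled rule is weak against a small group or late harm. Both points stand; they limit what the fix can promise.

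**Conclusion.** The point holds as a modest but worthwhile design improvement. The visible protocol tests acceptability without stating a tolerable rate, and provides neither a scheduled review of accumulated serious toxicity nor a count that pauses accrual.

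The size can only be illustrated. At a true 30% rate, about 15 of 50 patients would be affected with no planned check in the visible text. With 10% assumed tolerable, the example rule would pause in 95% of such trials (97% with a fifth look), at a cost of 7.3% (7.8%) false pauses. These figures require prompt events at one common rate. A reader might take them to mean that a pooled rule would reliably protect the re-irradiated groups; the calculation does not bear that out, since excess confined to 16 of 50 patients triggers a pause in only about 18%, and less often if harm is late.

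The absences are clear in the visible text. Whether local policy already fills the review gap cannot be determined from it.

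**What to change.** Amend 9.3 as follows.

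1. State a tolerable rate of treatment-related serious adverse events, each patient counted once. Keep this separate from the rate of any serious adverse events in 10.5.2: in recurrent cancer the two may differ widely.
2. State the period the rate covers, and use the same period for the count. It should be long enough to include the late events of 9.3.3; a 6-month window would miss much of that harm.
3. After every 10 treated patients, tabulate the cumulative count overall and for each of the three groups in 2.2.2. Keep adding late events in earlier patients until accrual closes.
4. Fix a pooled count that pauses accrual for IRB/HIC review. As an illustration only, if 10% is tolerable: 4/10, 5/20, 7/30, 8/40, counting only the first 40 patients, or the same with 10/50 added. Say which applies, so that patients 41–50 are covered by a stated rule.
5. Print the pause probabilities with their assumptions, say that late-onset or single-group excess is often missed, and have the investigators review the by-group table at every look.
6. If the IRB policy already requires cumulative review, cite it and add only the rate and the count.

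The cost is one paragraph, one small table, and four or five tabulations. The downside is about a 7–8% chance of a pause when toxicity is at the tolerable rate, and that pause leads to review, not closure.
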